## 10. STUDY CALENDAR

### Schedule of Study Assessments

Procedure	Screening 	Cycles -1, 1 and 2							
		24hrs before study drug	Day 1	Day 2	Day 4 (+/- 1)	Day 8	Day 11 (+/- 1)	Day 15	Day 22
Medical history assessment	X								
Interim history			X		X	X	X	X	X
Physical examination, vital signs	X		X		X	X	X	X	X
ECOG performance status, weight	X		X			X		X	X
Lymph node, spleen and liver assessment by physical exam 	X		X			X		X	X
CLL Flow Cytometry 	X								
interphase FISH (CLL Panel) 	X								
Purified CLL cell interface FISH	X								
IgVH Mutation Analysis	X								
BLyS/BAFF Analysis 			X 					X 	X 
IMiD™ compound studies and Methylation Arrays 			X 					X 	
RNA Expression Arrays 			X		X  Day 2			X	
Metabolomics			X 					X 	
T-cell Repertoire Studies 			X 						
PI 3-Kinase Assessment 			X 					X 	
Peripheral Blood Activation Markers: CD38, HLA-DR, CD25			X					X	
Peripheral Blood Cell Subset Analysis 	X		X 					X 	
VEGF Analysis			X			X			
Genetic polymorphisms	X								
Bone marrow assessment 	X								
CT of the chest / abdomen / pelvis 	X								
ECG	X								
Hematology 	X		X		X	X	X	X	X
Serum chemistries 	X		X		X	X	X	X	X
IFE, beta-2-microglobulin, DAT	X								
Pregnancy testing 	X	X	X 			X 		X 	X 
Register and comply with RevAssist® and S.T.E.P.S.® program	X	X							
Rituximab administration			X 			X 		X 	X 
Response assessment 									
Record adverse events 						X			X
Perform drug accountability			X						
Prescribe and dispense study drugs for next cycle 			X						

Procedure	Cycles 3, 4, 5, 6	Cycles 3, 4 and any Cycle where lenalidomide dose is escalated				
	Day 1	Day 4 (or) Day 3	Day 8	Day 11 (or) Day 10	Day 15	Day 22
Medical history assessment						
Interim history	X	X	X	X	X	X
Physical examination, vital signs, weight	X	X	X	X	X	X
ECOG performance status	X		X		X	X
Lymph node, spleen and liver assessment by physical exam 	X		X		X	X
Bone marrow assessment 						
Peripheral Blood Cell Subset Analysis 	X 					
CT of the chest / abdomen / pelvis 						
Hematology 	X	X	X	X	X	X
Serum chemistries 	X	X	X	X	X	X
Pregnancy testing 	X 				X 	
T-cell Repertoire Studies 	X 					
Comply with RevAssist® and S.T.E.P.S.® program	X					
Response assessment 	X					
Record adverse events 	X		X			X
Perform drug accountability	X					
Prescribe and dispense study drugs for next cycle 	X					

An unscheduled visit can occur at any time during the study. Source must be maintained for these unscheduled visits. The date for the visit and any data generated must be recorded on the appropriate CRF. Source documents for these unscheduled visits must also be maintained.

Procedure	Rituximab administration Cycles 7, 13, and 19				For all other cycles 8 and beyond 	Discontinuation From Protocol therapy
	Day 1	Day 8	Day 15	Day 22	Day 1	
Medical history assessment	X				X	
Interim history	X	X	X	X	X	
Physical examination, vital signs, weight	X	X	X	X	X	X
ECOG performance status	X	X	X	X	X	X
Lymph node, spleen and liver assessment by physical exam 	X	X	X	X	X	
Bone marrow assessment 						
BlyS/BAFF Analysis 	X				X 	
Peripheral Blood Cell Subset Analysis 					X 	
CD4/CD8/CD56 cell count						X
CT of the chest / abdomen / pelvis 	X				X 	X
Hematology 	X	X	X	X	X	X
Serum chemistries 	X	X	X	X	X	X
Pregnancy testing 	X 		X 		X 	X 
Comply with RevAssist® and S.T.E.P.S.® program	X				X	
T-cell Repertoire Studies 					X 	
IFE, beta-2-microglobulin, DAT	X				X 	
Response assessment 	X				X 	X
Record adverse events 	X	X	X	X	X	X 
Perform drug accountability	X				X	
Prescribe and dispense study drugs for next cycle 	X				X 	
Rituximab administration	X 	X 	X 	X 		
MRD status – peripheral blood assessment	X				X 	
Obtain Follow-Up anti-cancer treatments						F/u phase : Q 3 months
Obtain Follow-Up survival information						F/u phase : Q 3 months

 ≤ 28 days from baseline (First day study drug administration)

 To include iFISH for trisomy 12, deletion 17p, deletion 13q14, deletion 11q23; should be performed on peripheral blood and bone marrow

 BlyS/BAFF Analysis:

- Baseline: BlyS gene polymorphisms, MMP-9 activity
- Cycle -1 and 1; Days 1 & 15 prior to administration of study drug: serum levels of BlyS & APRIL, BlyS expression on monocytes, BlyS receptor expression on CLL cells
- Cycle 1, 7, 13, and 19 –immediately prior to Rituximab: serum levels of BlyS & APRIL

 IMiD™ compound Studies and Methylation Arrays:

- Cycle -1 and 1: Days 1 & 15 prior to administration of study drug: p38Mark activity, TNF-alpha/cox-2/BAFF mRNA levels, level of HuR binding to TNF-alpha/cox-2 mRNA/BAFF mRNA
- Cycle -1 and 1: Days 1 & 15 prior to administration of study drug: Changes in gene methylation patterns resulting from IMiD therapy by MOMA

 RNA Expression Arrays:

- Cycle -1 and 1: Days 1, 2 & 15 prior to administration of study drug: CLL cells, T cells, Monocytes

 Peripheral Mononuclear cell subsets

- **Prior to administration of study drug Days:** 1 and 15 of Cycle 1; Day 1 of Cycles 2 and 3; q 3 cycles through Cycle 24(cycle 6, 9, 12, etc.); then q 6 cycles thereafter: CD3/CD4/CD8-T cell subsets;

CD16/CD56- NK cells; CD14- monocytes; CD3/CD25/FoxP3-regulatory T cells; Circulating Endothelial cell precursors

-  To include WBC, differential, hemoglobin, hematocrit, platelets. Hematology profiles are required weekly during Cycle -1 of lenalidomide-containing therapy, and during any cycle in which the dose of lenalidomide is escalated or re-escalated. For subjects who are on a stable lenalidomide dose (without escalation or interruption) for  $\geq 1$  cycle of treatment, hematology profiles are required on Days 1 and 15 of the cycle.
-  To include Na, K, Cl, CO2, BUN, Cr, glu, Ca, phos, uric acid, LDH, alkaline phosphatase, total bilirubin, ALT, AST, albumin, total protein. At a minimum, for tumor lysis syndrome (TLS) monitoring purposes, subjects will have chemistry assessments weekly during at least the first 2 cycles of lenalidomide-containing treatment as well as on Day 3 or 4 of Cycle -1. In addition, because the risk for TLS may be elevated when lenalidomide is re-started after treatment interruptions or when the lenalidomide dose is escalated, in any cycle in which the lenalidomide dose is escalated, re-escalated, or treatment is interrupted for more than 1 week, subjects will have weekly chemistry assessments performed for at least 4 consecutive weeks, as well as an additional chemistry assessment on day 3 or 4 during the first week. For subjects who do not experience any abnormalities in serum chemistry assessments for 2 consecutive cycles while on a stable lenalidomide dose (without escalation or interruption) throughout these 2 cycles, the timing of chemistry assessments may be reduced to Day 1 and Day 15 in subsequent cycles.
-  Pregnancy tests required for females of childbearing potential. A female of childbearing potential (FCBP) is a sexually mature female who: 1) has not undergone a hysterectomy or bilateral oophorectomy; or 2) has not been naturally postmenopausal for at least 24 consecutive months (i.e., has had menses at any time in the preceding 24 consecutive months).
-  Pregnancy tests must occur within 10 – 14 days and again within 24 hours prior to initiation of lenalidomide and thalidomide. FCBP with regular or no menstruation must have a pregnancy test weekly for the first 28 days and then every 28 days while on therapy (including breaks in therapy); at discontinuation of lenalidomide/thalidomide and at day 28 post the last dose of lenalidomide/thalidomide. Females with irregular menstruation must have a pregnancy test weekly for the first 28 days and then every 14 days while on therapy (including breaks in therapy), at discontinuation of lenalidomide/thalidomide and at day 14 and day 28 post the last dose of lenalidomide/thalidomide (see Appendix A: Risks of Fetal Exposure, Pregnancy Testing Guidelines and Acceptable Birth Control Methods).
-  After cycle 24, clinic visits (and the corresponding assessments) are only required every 3rd cycle (e.g. Cycle 24, 27, 30, etc.). For any non-clinic visit treatment cycles (e.g. Cycle 25, 26, 28, 29, etc.), subjects must still meet all requirements for the initiation of a new treatment cycle, including compliance with the RevAssist® and S.T.E.P.S.® programs, and all pregnancy testing and pregnancy risk counseling requirements. Hematology assessment (see number 7) will be done locally as required for the initiation of a new treatment cycle.
-  CT scans should be done every six months for three years, and every twelve months thereafter. Response assessment and MRD assessment should be performed every six months subsequent to Cycle 24. Patients whose blood counts meet criteria of a CR should undergo a CT scan within 4 weeks. If CT scan supports a response of CR, then bone marrow examination and peripheral blood MRD assessment should be performed within 4 weeks.
-  An additional safety assessment will be done 28 days (+/- 2 days) following the last dose of study drug.
-  Only enough thalidomide and lenalidomide for 1 cycle of therapy may be provided to the patient each cycle. For non-clinic visit treatment cycles subsequent to Cycle 24 (e.g. Cycle 25, 26, 28, 29, etc.), study drug will be shipped to the subject at the start of each cycle.
-  Physical examination of lymphadenopathy, spleen and liver will be performed on Days 1, 8, 15, and 22 of Cycles -1, 1, 2, 3,4 and 5 to assess for tumor flare reaction, and on Day 1 of subsequent cycles starting with cycle 5 to assess response.
-  CLL Flow Cytometry should include markers for diagnosis and prognosis: CD5, CD19/CD20, CD23, CD38, sIg, and zap-70, by immunohistochemistry. Also IgVH Mutation Analysis, Purified CLL cell interphase FISH, beta 2 microglobulin
-  Rituximab administration starting with Cycle 1 and then every 6th cycle through Cycle 19 (i.e. 7, 13, and 19) on Days 1, 8, 15 and 22.
-  Metabolimics on Days 1 and 15 prior to study drug administration for Cycles -1 and 1.
-  T-cell Repertoire Studies: samples will be collected prior to treatment on cycle -1 and prior to cycles 6, 12, and 24 and evaluated for T-cell Repertoire
-  PI 3-Kinase Assessment: samples will be assessed for PI 3-Kinase activity levels prior to cycle -1, day 15 of cycle -1, and day 15 of cycle #1.
-  After Cycle 19, IFE, beta-2-microglobulin, DAT assessment will be done every 6 cycles starting with Cycle 24.

\*\*\*\* Rituximab can be given +/- 2days.

\*\*\*\*All correlative work must be drawn prior to Rituximab administration regardless of the day Rituximab is given.

## 11. MEASUREMENT OF EFFECT

Baseline lesion assessments must occur within  $\leq 28$  days of study drug administration or as indicated in Section 10, Schedule of Study Assessments.

Efficacy assessments are scheduled to occur every four weeks. It should be noted that signs and symptoms of a tumor flare may appear similar to disease progression. Investigators should decide whether apparent increases in disease are indicative of a tumor flare or disease progression. If the increases in lymphadenopathy, tenderness, leukocytosis, or cytopenias occur within four weeks of a dose escalation, then it is possible the changes are indicative of a disease flare. If these changes begin more than four weeks after a dose increase, then the changes are likely disease progression. These are guidelines to help investigator in making their decision, but the decision regarding classifying their disease as progression or flare remains ultimately with the investigator.

Response and progression will be evaluated in this study using the International Workshop on CLL (IWCLL) update of the 1996 NCI-Working Group criteria for CLL [15].

11.1 **Complete response:** requires all of the following conditions to be met:

1. Absence of clonal lymphocytes in the peripheral blood by flow cytometry.
2. Blood counts above the following values:
  - a) neutrophil count  $> 1500/ \text{mm}^3$ , without the use of growth factors
  - b) hemoglobin  $> 11 \text{ gm/dL}$ , untransfused (men and women)
  - c) platelet count  $> 100,000/ \text{mm}^3$ , untransfused
3. Absence of lymphadenopathy on CT examination of the neck, chest, abdomen, and pelvis (lymph nodes  $< 1.5 \text{ cm}$  in diameter).
4. Absence of hepatomegaly or splenomegaly by CT examination
5. Absence of constitutional symptoms.
6. Bone marrow biopsy and aspirate demonstrating normal cellularity for the age of the patient and free of clonal CLL cells by conventional (not 4-color) flow cytometry and / or immunohistochemistry. If lymphoid nodules are present (formerly nPR), they should be assessed by immunohistochemistry to determine whether they are composed of CLL cells. If the lymphoid nodules are not CLL cells, then the patient will be considered a CR. If the lymphoid nodules are composed of CLL cells, then the patient will be categorized as a PR. If the bone marrow is found to be hypocellular, a repeat marrow biopsy should be performed after 4-6 weeks.
7. Patients who fulfill all of the criteria for CR, including marrow examination, but who have persistent anemia or thrombocytopenia, or neutropenia unrelated to CLL but related to drug toxicity will be characterized as CR with incomplete marrow recovery (CRi). These patients will be followed in order to determine whether their prognosis differs from

patients in CRs or PRs.

11.2 **Partial response:** any response less than a complete response but still meeting the following criteria:

1. 50% decrease in peripheral blood lymphocytes from the pre-treatment value.
2. 50% reduction in lymph node size by CT examination as measured by the sum of the products of up to 6 lymph nodes, or in one lymph node diameter if only a single lymph node is present.
3. No increase in the size of any lymph node, and no new enlarged lymph nodes, by CT examination.
4. 50% reduction in the size of the liver and / or spleen by CT examination
5. Blood counts must show one of the following:
  - a) neutrophil count  $\geq 1500/\text{mm}^3$  or 50% improvement over baseline without the use of growth factors.
  - b) hemoglobin  $> 11.0 \text{ gm/dL}$  or 50% improvement over baseline without transfusions or erythropoietin support.
  - c) platelet count  $> 100,000/\text{mm}^3$  or 50% improvement over baseline without transfusions.

11.3 **Progressive disease:** any of the following characteristics:

1. Progressive lymphadenopathy, as defined by:
  - a) Appearance of any newly enlarged lymph nodes to  $> 1.5 \text{ cm}$ .
  - b) An increase by 50% or more in greatest diameter of any previous site of disease. For a lymph node of 1 to 1.5 cm must increase by at least 50% to a size greater than 1.5 cm. A lymph node greater than 1.5 cm in diameter must increase to more than 2.0 cm in diameter.
  - c) An increase of 50% or more in the sum of the products of diameters of multiple lymph nodes.
2. An increase in liver or spleen size by 50% or more or the appearance of new hepatomegaly or splenomegaly.
3. An increase in the number of blood lymphocytes by 50% or more with at least 5000 B lymphocytes  $/\text{mm}^3$ .
4. Transformation to a more aggressive histology.
5. Occurrence of cytopenias attributable to CLL, excluding those related to therapy or autoimmune phenomenon. The progression of any cytopenia is defined by:

- a) decrease in Hb by more than 2 g/dL or to less than 10 g/dL.
- b) decrease in platelet counts by more than 50% or to less than 100,000/ mm^3.

11.4 **Stable disease:** patients who have not achieved a CR or a PR, and who have not exhibited progressive disease, will be considered to have stable disease.

11.5 **Relapse:** patients who has previously achieved a CR or PR, but after a period of 6 or more months, demonstrate evidence of disease progression.

11.6 **Refractory disease:** disease progression within 6 months of the last treatment.

11.7 **Duration of response definitions:**

1. **Duration of response:** from the end of the last treatment until evidence of progressive disease.
2. **Time to response:** interval from the first treatment day to the date response first identified.
2. **Progression-free survival:** interval between the first treatment day and the first sign of disease progression.
3. **Event-free survival:** interval between the first treatment day to the first sign of disease progression, treatment for relapse, or death, whichever occurs first.
4. **Survival duration:** interval between the first day of treatment and death

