#### **Hematopoietic Growth Factors**

Myeloid growth factors (G-CSF and pegfilgrastim only) may be used. GM-CSF may not be used given the theoretical impact it might have on CLL disease activity. Erythropoietic Stimulating Agents (ESAs; Aranesp, Procrit) may be used at the discretion of the treating physician and need to be recorded in the medication list.

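### The CR haemoglobin criterion does not exclude erythropoietin support, so a patient with drug-related anaemia can be counted as full CR instead of CRi; ORR and the decision rules are unaffected

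*Combined protocol and SAP*

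**What the plan says.** All references are to the combined protocol and SAP.

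- **CR, Section 11.1.** The definition "requires all of the following conditions to be met". Item 2b sets haemoglobin above 11 g/dL, "untransfused (men and women". The phrase "without the use of growth factors" appears in item 2a, on the neutrophil line only. Item 7 creates CRi for patients who fulfil the CR criteria, marrow included, but have a persisting cytopenia due to drug toxicity. It says their prognosis will be compared with that of CR and PR patients.
- **PR, Section 11.2 item 5.** "Blood counts must show one of the following": neutrophils, haemoglobin or platelets. The haemoglobin line (5b) accepts a value above 11.0 g/dL "or 50% improvement over baseline without transfusions or erythropoietin support".
- **Supportive care, Section 5.5.1, Hematopoietic Growth Factors.** Erythropoietic agents "may be used at the discretion of the treating physician and need to be recorded in the medication list".
- **Study calendar, Section 10, footnote 12.** "Patients whose blood counts meet criteria of a CR should undergo a CT scan within 4 weeks"; if the CT agrees, marrow examination and a blood MRD assessment follow.
- **Use of the CR rate.** The primary objective (Section 1.1) names overall, complete and partial response. Section 13.3 estimates all three with a 95% interval. The tested endpoint (Sections 1.3 and 13.1) is CR + PR.

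**The concern.** The stricter response category has the looser haemoglobin rule. The authors treated erythropoietin support as a distortion of the haemoglobin reading when they wrote PR, but did not carry the exclusion into CR, and no other section supplies it.

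The situation can plausibly arise. Anaemia is among the frequent lenalidomide events listed in Section 2.3. Worsening anaemia is one of the treatment indications at entry (Section 3.1), and the laboratory criteria set no haemoglobin floor. Response is judged while patients remain on drug, and best response is what counts.

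Consider a patient with a clear marrow and drug-related anaemia. Below the haemoglobin threshold, this patient is CRi. If an erythropoietic agent lifts haemoglobin above 11 g/dL, the same patient reads as full CR, although neither the disease nor the underlying drug toxicity has changed. At stake are the CR rate, which is a reported estimate under the primary objective, and the CR/CRi comparison that item 7 sets up.

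**Working it through.** **1. The plan's own figure.** Section 13.1 gives a two-stage rule: stop if 6 or fewer of 11 respond; declare effective if 18 or more of 24 respond; p0 = 0.60, p1 = 0.80, 10% significance, 80% power. With X1 ~ Bin(11, p) and X2 ~ Bin(13, p),

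P(positive) = Σ over x = 7 to 11 of P(X1 = x) × P(X2 ≥ 18 − x).

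- At p = 0.60: 0.0930 (limit 0.10); probability of early stopping 0.467.
- At p = 0.80: 0.8015 (target 0.80).

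A full search finds 24 as the smallest total size, with 6/11 and 17/24 as the minimax boundaries. The design reproduces. It counts CR + PR, so the question is whether the haemoglobin wording changes who is counted.

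**2. Apply the criteria to one patient.** Illustrative values: neutrophils 1800/mm³ without growth factors, platelets 150,000/mm³ untransfused, haemoglobin 11.5 g/dL on an erythropoietic agent, no transfusion, all other CR items met.

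| Criterion | As written | With erythropoietin excluded in 2b |
|---|---|---|
| CR 2a, neutrophils > 1500 | met | met |
| CR 2b, haemoglobin > 11 | met | not met |
| CR 2c, platelets > 100,000 | met | met |
| **CR** | **yes** | **no** |
| PR 5a, neutrophils | met | met |
| PR 5b, haemoglobin | not usable | not usable |
| PR 5c, platelets | met | met |
| **PR item 5 (one of three)** | **met** | **met** |

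The patient is a responder in both columns. This takes PR items 1 to 4 as met by someone who has cleared clonal lymphocytes, nodes and organs to the CR standard. Change in ORR: 0 points. Only the label moves: to CRi under item 7 if the anaemia is drug-related, otherwise to PR.

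**3. Size for the CR rate.** Each relabelled patient changes it by 1/24 = 4.17, or 4.2, percentage points, provided CRi is not pooled with CR. The documents give neither an expected CR count nor a rate of erythropoietic use, so the counts below are assumptions. Section 13.3 does not name the interval method; Clopper-Pearson is used here.

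| CR count | Rate | 95% interval |
|---|---|---|
| 6/24 | 25.0% | 9.8 to 46.7 |
| 5/24 (one relabelled) | 20.8% | 7.1 to 42.2 |
| 4/24 (two relabelled) | 16.7% | 4.7 to 37.4 |

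**4. Follow the assessment path.** Footnote 12 starts the CT and marrow sequence when the blood counts meet CR. Item 7 requires a marrow examination before CRi can be assigned. If 2b is tightened and nothing else changes, an agent-supported patient no longer meets the CR counts, and footnote 12 no longer leads to the marrow that CRi needs. The two provisions must therefore be changed together.

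**The case against.** The case against giving this weight has several parts.

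- **No trial decision changes.** This stands. A reader might infer that supportive care could push the trial over 7/11 or 18/24. The documents do not support that: PR item 5 is already met on neutrophils or platelets.
- **PR does not bar these patients.** This also stands. A reader might infer that a patient on an erythropoietic agent qualifies for CR but is shut out of PR. Item 5b only stops that haemoglobin from serving as the one qualifying count. Its qualifier could even be read as attached to the 50% improvement branch alone. On that reading PR would still exclude erythropoietin somewhere and CR nowhere.
- **CRi might be reported within CR.** Item 7 sits inside Section 11.1, and nothing says CRi is left out of the CR rate. If it is pooled, relabelling from CR to CRi changes nothing. This limits the size and is itself a gap to close.
- **Item 7 may already cover the case.** It sets no haemoglobin cut-off, so an investigator could class a patient on continuing support as CRi. That is possible but discretionary; the written CR items would still be met.
- **Section 11 cites the IWCLL update.** What that source says cannot be checked here. The protocol writes out its own criteria and does not say that the source overrides them.
- **Use is discretionary and recorded.** So affected patients can be identified. CR also still demands no clonal blood lymphocytes, CT clearance and a CLL-free marrow, none of which an erythropoietic agent supplies.

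**Conclusion.** The gap is real and narrow. Followed as written, Section 11.1 item 2b lets an agent-supported haemoglobin count towards full CR, and a patient with drug-related anaemia who meets all other CR items can be recorded as CR rather than CRi because of supportive care alone. The effect is confined to the CR versus CRi/PR split: up to 4.2 points of the CR rate per affected patient, on the assumption that CRi is reported separately. How many patients would be affected is unknown. ORR and the Simon rules are unaffected. The correction is worth making because the CR rate is named in the primary objective and estimated with an interval, and the change costs little.

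**What to change.** 1. In Section 11.1 item 2b, replace the transfusion-only qualifier with one that excludes both transfusion and erythropoietin support, using the terms of Section 11.2 item 5b. Make clear in 5b that the exclusion covers both branches.
2. State that patients who otherwise meet CR but rely on such support for drug-related anaemia are CRi.
3. State that CRi counts as a response in ORR and is reported separately from CR. Without this, the relabelling could be misread as removing responders.
4. Reconcile footnote 12 of the study calendar with item 7, so that CRi candidates still reach the CT and marrow assessments on which CRi depends.
5. Apply the rule from the medication list already kept, including to patients already enrolled, and show the CR rate with and without erythropoietic support.

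The cost is a few sentences and possibly a slightly lower reported CR rate. The change concerns response classification only, not who may receive these agents.

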#### **3.1 Inclusion Criteria**

1. Confirmed diagnosis of CLL or SLL based upon standard criteria as outlined in the IWCLL Update of the 1996 NCI-Working Group criteria for CLL [15]:
  - a) Presence of one of the following:
    1. more than or equal to  $5 \times 10^9$  B lymphocytes/L in the peripheral blood for a duration of at least 3 months. Patients with a B lymphocytosis will be characterized as CLL, while those without will be characterized as SLL
    2. the presence of lymphadenopathy resulting from infiltration with lymphocytes with the phenotype of CLL
    3. bone marrow infiltration with lymphocytes with the phenotype of CLL
  - b) Lymphocytes with the morphologic appearance of small, mature appearing lymphocytes, with  $\leq 55\%$  prolymphocytes (blood or bone marrow)
  - c) Cellular phenotype characterized by the:
    1. co-expression of the CD5, CD20, and CD23 surface antigens
    2. clonal kappa or lambda light chain expression

3. dim surface immunoglobulin expression
2. No prior therapy for CLL, including treatment for autoimmune conditions that have developed since the initial diagnosis of CLL.
3. Active disease requiring therapy as defined by the IWCLL Update of the 1996 NCI-WG guidelines [15]:
  - a) Evidence of progressive marrow failure as manifested by the development of worsening of anemia and / or thrombocytopenia
  - b) Massive, progressive, or symptomatic splenomegaly
  - c) Massive, progressive, or symptomatic lymphadenopathy
  - d) Progressive lymphocytosis with an increase of more than 50% over a 2-month period or a lymphocyte doubling time of less than 6 months.
  - e) Autoimmune anemia and/or thrombocytopenia poorly responsive to corticosteroids or other standard therapy
  - f) Presence of disease related symptoms: unintentional weight loss of more than 10% within previous six months, significant fatigue, fevers greater than 100.5 F or 38.0 C for 2 or more weeks without evidence of infection, night sweats for more than 1 month without evidence of infection.
4. Understand and voluntarily sign an informed consent form.
5. Age  $\geq 18$  years at the time of signing the informed consent form.
6. Able to adhere to the study visit schedule and other protocol requirements.
7. ECOG performance status of  $\leq 2$  at study entry (see Appendix B).
8. Laboratory test results within these ranges:
  - Absolute neutrophil count  $\geq 1000/\text{mm}^3$
  - Platelet count  $\geq 50,000/\text{mm}^3$

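### Read literally, the organ rule for partial response (11.2 item 4) can be stricter than the organ rule for complete response, so a patient whose liver or spleen has returned to normal can be classed as stable disease

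*Combined protocol and SAP*

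**What the plan says.** All the classification rules are in Section 11 of the combined protocol and SAP.

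- **CR, 11.1 item 4:** "Absence of hepatomegaly or splenomegaly by CT examination". Return to normal size is enough.
- **PR, 11.2:** the category is defined as "any response less than a complete response but still meeting the following criteria". Five items follow, and only item 5 (blood counts) lets the patient meet one of several alternatives. Item 4 reads "50% reduction in the size of the liver and / or spleen by CT examination". It gives no normal limit, does not say whether size means length, area or volume, and is not restricted to organs enlarged at baseline.
- **Marrow nodules, 11.1 item 6:** "If the lymphoid nodules are composed of CLL cells, then the patient will be categorized as a PR".
- **Progression, 11.3 item 2:** "An increase in liver or spleen size by 50% or more or the appearance of new hepatomegaly or splenomegaly".
- **Default category, 11.4:** "patients who have not achieved a CR or a PR, and who have not exhibited progressive disease, will be considered to have stable disease".
- **Reference criteria, opening of Section 11:** "Response and progression will be evaluated in this study using the International Workshop on CLL (IWCLL) update of the 1996 NCI-Working Group criteria". The documents neither reproduce that text nor say which wording prevails if it differs from 11.1 to 11.5.

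The primary endpoint is ORR (CR + PR) at best response (Section 1.3). Under Section 13.1 the trial continues with at least 7 responders among 11 and is positive with at least 18 among 24. Organ enlargement is one of the listed reasons for needing treatment: "Massive, progressive, or symptomatic splenomegaly" (Section 3.1, item 3b).

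**The concern.** A lower response category should not carry a harder test than the category above it. Here it can, because the CR rule looks at whether enlargement is gone, while the PR rule looks at the proportional change in the organ. A normal liver or spleen still has a size, so an enlarged organ can normalise without halving.

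This matters only for a patient who misses CR on some other item and must qualify through 11.2. If item 4 then fails, 11.4 makes that patient stable disease, a non-responder for the primary endpoint. The error runs in one direction, toward a lower ORR, and the decision rests on small counts: one patient in 24 is 1/24 = 4.2 percentage points. Since splenomegaly is a route into the trial, affected patients are foreseeable.

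**Working it through.** **1. The plan's own figures.** Inputs from Section 13.1: null rate 0.60, target rate 0.80, 10% significance level, 80% power, continue if at least 7/11 respond, positive if at least 18/24 respond. With response rate p,

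P(positive) = sum over x = 7 to 11 of C(11,x) p^x (1-p)^(11-x) × P[Bin(13,p) ≥ 18 - x].

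This gives 0.093 at p = 0.60 and 0.801 at p = 0.80. A search over two-stage designs returns the same minimax design (11 then 24, with cut-offs 6 and 17). The design figures are sound.

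**2. The organ rules side by side.** Let the baseline organ be k times its upper normal limit on whatever CT measure is used. Returning to that limit is a reduction of 1 - 1/k.

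| k | Reduction on return to the normal limit | CR organ rule | PR organ rule, literal |
|---|---|---|---|
| 1.25 | 20% | met | not met |
| 1.5 | 33% | met | not met |
| 1.75 | 43% | met | not met |
| 2.0 | 50% | met | met |
| 2.5 | 60% | met | met |

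The crossover is exactly k = 2 and needs no outside figure. An organ that shrinks further below the limit does somewhat better than the table shows.

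**3. Who can be lost.** Take an organ with k below 2 that has normalised without halving, in a patient who meets the other PR items but misses CR because:
- clonal lymphocytes are still found by flow cytometry (11.1 item 1);
- a node of 1.5 cm or more remains after the nodes have halved (item 3); or
- constitutional symptoms remain (item 5).

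None of these has its own route to PR. Item 4 fails, and 11.4 gives stable disease.

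**4. Dependence on the measure.** The documents give no normal spleen size; 12 cm is assumed here for illustration. For a spleen going from 18 to 12 cm:
- by length: 1 - 12/18 = 33%, fails;
- by cross-product, with proportional shrinkage (assumed): 1 - (12/18)² = 56%, passes;
- by volume, on the same assumption: 1 - (12/18)³ = 70%, passes.

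The same scan therefore gives different answers, and the protocol does not choose between them. The inversion remains on every measure, but the affected range of baseline sizes differs.

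**5. What a loss would cost.** Suppose a share m of true responders is lost, so the observed rate is p(1 - m). The documents give no value for m; these are illustrations.

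| m | Observed rate if true rate 0.80 | P(positive) | P(positive) if true rate 0.60 |
|---|---|---|---|
| 0 | 0.800 | 0.801 | 0.093 |
| 2% | 0.784 | 0.741 | 0.075 |
| 5% | 0.760 | 0.641 | 0.053 |
| 10% | 0.720 | 0.464 | 0.028 |

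**6. After the fix.** If the 50% is taken on the enlargement (baseline size minus the upper normal limit), return to the limit is a 100% reduction for every k above 1. An organ that meets the CR rule then cannot fail the PR rule. In the 18 cm example with an assumed 12 cm limit, the PR threshold becomes (18 + 12)/2 = 15 cm.

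**The case against.** **The reference criteria may govern.** Section 11 says response follows the IWCLL update, and assessors might apply that text instead of item 4 as written. This is possible, but Section 11 then sets out its own criteria and gives no order of precedence. Two assessors could classify the same patient differently.

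**Size is not defined.** Whole-organ size is a reading, though a natural one: 11.3 item 2 uses size and new enlargement as separate ideas in one sentence. A volume measure would bring many more spleens past 50%. This limits the reach of the problem without removing it.

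**One organ may suffice.** The wording can be read so that a single organ qualifies. That does not help when the only enlarged organ normalises from below twice normal.

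**Few patients may be affected.** A lost responder must have an organ below twice normal at baseline, miss CR, meet every other PR item, and do so at every assessment, because ORR is taken at best response. This stands. The loss also makes a false positive less likely.

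Three stronger readings are tempting, and the documents do not support them:
- *That patients with CLL nodules in the marrow are refused PR by item 4.* Item 6 of 11.1 assigns them to PR directly.
- *That normalised organs usually fail item 4.* The documents give no baseline organ sizes, normal limits or frequency of enlargement.
- *That PFS is materially delayed by the same use of size in 11.3.* Progression is met by any one of several findings, and Section 13.3 also counts symptomatic progression.

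**Conclusion.** Wrong as written. The PR organ rule, read literally, can be harder to meet than the CR organ rule for any organ below twice its normal limit at baseline on the measure used. A patient in that position who misses CR on another item can be recorded as stable disease and dropped from ORR. The direction of the bias is certain: downward.

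Its size cannot be derived from the documents. It depends on the CT measure, the distribution of baseline organ sizes, and whether assessors follow Section 11 or the cited criteria. The power figures show how sensitive the design is to a small loss; they do not predict one. A reader might infer that the trial is badly underpowered; that would need a known loss rate, which the documents do not give.

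**What to change.** Reword 11.2 item 4 so that, for organs enlarged at baseline, the patient needs either a reduction of at least 50% in the baseline enlargement (measured size minus the upper normal limit) of the liver and/or spleen, or a return to normal size, on CT. The restriction to organs enlarged at baseline also settles the position of patients whose organs were normal at entry, on which item 4 is silent. State one CT measure and one upper normal limit per organ, and say whether Section 11 or the cited IWCLL criteria prevail.

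Do not reword 11.3 item 2 on the same basis. Progression ends treatment (Section 5.6), and close to the normal limit a very small change would trigger it: with an assumed 13 cm limit, a 14 cm spleen would progress at 14.5 cm. Note only that its use of size must be reconciled with the measure chosen.

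The cost is protocol wording and, where needed, re-reading existing scans. The small downside is that easing a response rule in an open-label, single-arm trial can look like raising ORR after the fact. Document the change and its date and, if responses have already been assessed, report ORR under both readings. The sample size and the 7/11 and 18/24 rules need no change.
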